Change from baseline in presence and severity of symptoms (5-point severity scale), clinical signs (3-point severity scale) and architectural changes (3-point severity scale) at the 6-week, 3-month, 6-month and 12-month follow-up visits. (**Appendices I & II**).

Secondary Safety Endpoints

Evaluate the safety of the treatment:

1. Clinical evaluation of treated area at each study visit. Clinical photography will be performed for study documentation (**Appendix IV**).
2. Pain/discomfort level using a 10-point Numerical Scale Response (NSR) after each treatment (**Appendix V**).
3. Number, severity and type of adverse events recorded throughout course of the study.
4. 1 week ± 2 days post first treatment safety phone call (review of 1-week patient diary) – (**Appendix VI**).

Secondary Efficacy Endpoints

1. Sexual function, using the Female Sexual Function Index (**Appendix III**), at baseline and at the 3-month and 6-month follow-ups. *An overall score ≤ 26.55 is classified as Female Sexual Disorder (FSD).*¹⁵
2. Histological signs (degree of hyperkeratosis, epidermal atrophy and dermal inflammation) at baseline and at 6 weeks and 6 months after the final treatment.
3. Subject satisfaction, using a 5-point Likert scale (-2=very dissatisfied; 2=Very satisfied), will be assessed at the 6-week, 3-month, 6-month and 12-month follow-up visits (**Appendix VII**).

SUBJECT POPULATION

Up to 45 female subjects who meet the following inclusion / exclusion criteria may be enrolled.

Subject Withdrawal and Replacement

Subjects enrolled in the study can discontinue their participation at any time for any reason without prejudice or reduction in the quality of their medical care. The investigator or sponsor can terminate a subject's participation in this study to protect the subject's health or if the subject fails to follow directions resulting in noncompliance to study procedures. Subjects who withdraw or are terminated from the study may be replaced to allow up to 45 subjects to complete the study. Subjects who fail to complete the treatment will be replaced and will not be evaluable.

Inclusion Criteria

1. Able to read, understand and sign informed consent for study participation;
2. Female subjects with age 18-80 years;
3. Biopsy demonstrates biopsy-proven lichen sclerosus and/or there are characteristic changes for vulvar lichen sclerosus on physical examination;

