Table 2. Study Measurements

Assessment	When to conduct	Method
Complete the Inform Consent form and Eligibility Screening and Medical History	During the screening visit / prior to the 1 st treatment	Physician or staff will complete the form with the study subject
PAP smear if not up-to-date (within 3 years according to ACOG guidelines)		Patient should provide lab results of up-to-date normal cell cytology
Urine pregnancy test for women capable of becoming pregnant		Patient should have a negative pregnancy test
Gynecological exam		Physician will examine the vulvar and vaginal area for any signs of active infection or atypical nevi
Vulvar biopsy of treatment area (optional)	Prior to the 1 st treatment and at the 6-week and 6-month follow-ups	Biopsies will be obtained from up to 10 subjects to conduct histological assessment. Lab reports will be provided to show changes in markers compared to baseline.
Subject assessment of symptoms	
 • Baseline or pre-Tx. 1 • At the 6-week, 3-month, 6-month and 12-month follow-up visits 	Subjects will complete the Symptom Severity Questionnaire, according to the pre-defined scales (Appendix I)
Physician assessment	
 • Baseline or pre-Tx. 1 • Prior to treatments • At the 6-week, 3-month, 6-month and 12-month follow-up visits 	Physician will assess clinical signs associated with VLS, according to the pre-defined scales (Appendix II)
Subject assessment of sexual function	
 • Baseline or pre-Tx. 1 • At the 3-month and 6-month follow-up visits 	Subjects will complete the Female Sexual Function Index (FSFI) – Appendix III
Clinical evaluation and photographs of treated area	
 • Baseline or pre-Tx. 1 • Prior to treatments • At the 6-week, 3-month, 6-month and 12-month follow-up visits 	Physician will evaluate the treatment area. Physician or staff will take photographs of the treatment area (Appendix IV)
Treatment pain assessment	Immediately after each treatment	NSR Scale (Appendix V)
Subject 1-week daily diary - reviewed at the 1wk FU after the first treatment	The daily diary will be provided at the 1 st treatment visit and reviewed by phone during the 1-week safety evaluation	Subjects will be requested to complete a daily diary with data regarding their comfort, AE, and activity (7 days of follow-up post 1st treatment) – Appendix VI

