The biopsy specimen should be taken from the area of the vulva or peri-anal skin that clinically appears to have the most active or developed VLS changes. A 3-mm or 4-mm punch can be used in most cases. A 3-mm punch biopsy is generally thought to be the smallest size that will provide an adequate sample of tissue for pathologic analysis. However, certain locations where there is little subcutaneous adipose tissue, such as the labia minora and the clitoral hood, may be best sampled by scissor snip technique. The chosen location and biopsy technique should be based on the provider's best judgment of potential histological change as well as patient comfort and healing. Adjacent skin of the same area should be sampled for post-treatment follow-up biopsies.

Mark the biopsy site with surgical skin marker and photograph the marked location. To minimize patient discomfort, apply topical anesthetic prior to injecting local anesthetic. Then, draw 1ml of 1% lidocaine with 1:100,000 epinephrine into a 1ml syringe. Slowly inject the anesthetic with a 30-gauge needle. While this amount of local anesthetic is adequate for the majority of patients, additional anesthetic can be injected as clinically warranted. When anesthetizing the area, insert the needle and withdraw the plunger to decrease the chance that injection occurs into a vessel. Inject slowly at the base of and underneath the lesion, injecting enough to create a wheal. If possible, only penetrate the skin once. The wheal should be larger than the biopsy instrument that will be used. Adequate anesthesia for the procedure should be present in 1-2 minutes. Test for appropriate anesthesia prior to making any incision. As in most clinical situations, biopsy is performed shortly after injection.

Once an adequate biopsy sample has been excised, the specimen should be placed carefully in a fixative solution, such as 10% formalin. Confirm that the sample is in the container after closing the lid. The tissue should be sent to pathology along with the properly completed pathology forms. Insurance information should not be included on the form, as study subjects will not be billed for biopsies. Patient Initials and Subject Code should be included on the specimen labels (i.e. 001_AMK).

Hemostasis may be achieved with pressure only for small specimens. In addition to pressure, bleeding also may be controlled with suture or gel foam for punch biopsies or with aluminum chloride or silver nitrate for scissor snip biopsies.

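### Baseline biopsies go where disease looks worst and follow-up biopsies to neighbouring skin with no matching rule, so histological change may be biased towards improvement; random allocation of pre-marked spots would cheaply remove part of this

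*Protocol*

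**What the plan says.** The Protocol's Vulvar Biopsy Procedure gives different siting rules for the two sides of one within-subject comparison.

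- **Baseline:** the specimen is taken "from the area of the vulva or peri-anal skin that clinically appears to have the most active or developed VLS changes". Within that, "The chosen location and biopsy technique should be based on the provider's best judgment of potential histological change", with patient comfort and healing also to be weighed.
- **Follow-up (6 weeks and 6 months):** "Adjacent skin of the same area should be sampled for post-treatment follow-up biopsies". The section does not say how near adjacent means, and does not require the later site to resemble the baseline site in severity.
- **Documentation:** "Mark the biopsy site with surgical skin marker and photograph the marked location".

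Histology is the second of the Secondary Efficacy Endpoints: "Histological signs (degree of hyperkeratosis, epidermal atrophy and dermal inflammation) at baseline and at 6 weeks and 6 months after the final treatment". Table 2 sets the subset size ("Biopsies will be obtained from up to 10 subjects to conduct histological assessment") and the comparison ("Lab reports will be provided to show changes in markers compared to baseline"). The study has one group, and no untreated comparison site or second baseline specimen is described. The Protocol states no test, error rate or effect size for histology.

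**The concern.** A site chosen because it looks severe tends to be worse than its neighbours, to the extent that appearance predicts histology. If the baseline punch is chosen that way and the later punches are chosen only for lying beside it, the later specimens will on average look better whether or not the laser works. With no comparator, the data cannot separate this from a treatment effect, and the tilt applies at both follow-up times.

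Histology is the trial's only tissue-level evidence. A subset of at most 10 subjects gives little room to detect or adjust for such a tilt. The use of neighbouring skin is not itself the fault, because an excised site cannot be sampled again. The fault is that the two sides of the comparison are chosen by unequal rules.

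**Working it through.** The Protocol has no histology figure to reproduce. The check asks how large an apparent improvement arises from siting alone, with the true laser effect set to zero.

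**Inputs from the Protocol:** n = 10 (the upper limit of the subset), a within-subject comparison with baseline, and no control.

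**Assumed inputs (none is in the documents):** K, the number of candidate spots from which the visibly worst is taken; r, the correlation of clinical appearance with histology; and rho, a correlation defined separately in Models A and B. Bias is in SD units of a notional histology score. The expected maximum of K independent standard normals, E(K), is 0.846 for K = 3, 1.163 for K = 5 and 1.539 for K = 10.

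**Model A: rho is the correlation of baseline with follow-up histology, covering both distance and time.** Bias = r × E(K) × (1 − rho).

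- Smallest case for rho = 0.5: 0.3 × 0.846 × 0.5 = 0.13 SD.
- Largest case for rho = 0.5: 0.7 × 1.539 × 0.5 = 0.54 SD.

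| rho | Bias over K = 3 to 10, r = 0.3 to 0.7 | Simulated false-positive rate |
|---|---|---|
| 0.5 | 0.13 to 0.54 SD | 5% to 36% |
| 0.8 | 0.05 to 0.22 SD | 4% to 16% |
| 0.95 | 0.01 to 0.05 SD | 3% to 7% |
| 1 | 0 | not defined |

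**Model B: rho is the correlation between neighbouring spots, and follow-up is taken from one of the other K − 1 spots with no change over time.** Bias = r × E(K) × K/(K − 1) × √(1 − rho).

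- K = 3, r = 0.8, rho = 0: 0.8 × 0.846 × 1.5 = 1.02 SD.
- K = 5, r = 0.8, rho = 0: 0.8 × 1.163 × 1.25 = 1.16 SD.
- K = 3, r = 0.5, rho = 0.5: 0.5 × 0.846 × 1.5 × 0.707 = 0.45 SD.
- K = 5, r = 0.8, rho = 0.8: 0.8 × 1.163 × 1.25 × 0.447 = 0.52 SD.
- K = 3, r = 0.5, rho = 0.95: 0.5 × 0.846 × 1.5 × 0.224 = 0.14 SD.

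For K = 3 to 5 and r = 0.5 to 0.8, the simulated false-positive rate is about 28% to 83%. It hardly depends on rho, because this model has no time variation and the SD of the paired difference shrinks along with the bias.

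**Model C: the area is chosen for looking worst, both punches are random within it, and disease is stable.** Bias is 0.00 SD and the false-positive rate stays at 2.5%.

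**Effect of random allocation.** Repeating Model B with the baseline and follow-up spots drawn at random from the same set gives a bias of 0.00 SD and a false-positive rate of 2.3% to 2.7% in every scenario run.

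The false-positive rates are for a paired t-test with n = 10, counting the improvement direction only (nominal 2.5%). They are illustrative, since the Protocol specifies no such test.

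**The case against.** The strongest reply is that the Protocol selects an area, not a spot. The severity rule ("that clinically appears to have the most active or developed VLS changes") describes the area, all three biopsies stay in it, and nothing tells the provider to punch its worst point. This stands as far as it goes: under Model C the spatial bias is zero. It does not settle the matter, because the Protocol does not make the punch random either. Siting by judgment of likely histological change, with a 3-mm or 4-mm punch, leaves room for the provider to favour the most affected point.

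A reader might infer that histology will improve on paper even if the laser does nothing. The documents do not support that certainty. Whether within-area selection happens is not fixed by the text, the plausible size starts at nil, and a follow-up punch beside an earlier biopsy wound could show scarring, which the section lists as a risk. Even the net direction is therefore not assured.

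A reader might also quote the high false-positive rates as the trial's own error rate. They assume a worst-of-K punch, one summary score and a paired t-test. The Protocol names three separate histological signs, and a site that looks active need not be extreme on all of them.

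Finally, the reach is limited. The endpoint is secondary, the biopsy is optional, and the primary endpoint uses no biopsy.

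**Conclusion.** The point holds as a cheap improvement. The siting rules are unequal, no severity matching is required, and there is no comparator. If the baseline punch goes where disease looks worst within the chosen area, and appearance predicts histology at all, this selection biases change from baseline towards apparent improvement.

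The documents do not allow the amount to be fixed. Under the stated assumptions it runs from nil (punches effectively random within the area), through about 0.01 to 0.5 SD (baseline and follow-up correlation 0.95 down to 0.5), to about 1 SD if neighbouring spots are nearly uncorrelated and appearance tracks histology closely. The consequence is confined to the histology endpoint in up to 10 subjects.

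**What to change.** Amend the Vulvar Biopsy Procedure so that, at baseline, the investigator marks, maps and photographs three clinically comparable spots within the chosen area. A random list then assigns one spot each to the baseline, 6-week and 6-month biopsies. Investigator discretion for comfort and healing is kept, and is exercised when the spots are marked, before the list is consulted.

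The cost is a short random list and one site map for each biopsy subject. The number of biopsies is unchanged, and marking and photography are already required. The downside is that the baseline specimen will not always be the most affected point.

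The change removes only selection within the area. The area is still chosen at baseline for looking worst, and the Protocol's Background describes a relapsing disease, so regression to the mean over time remains. The Protocol should therefore also say that histological change will be reported descriptively, without attributing it to the laser.

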All data will be recorded on Case Report Forms (CRFs) or transcribed from source documentation, where applicable (i.e. lab reports). The site will be monitored by Syneron Candela staff or designees to assure adherence to the clinical trial requirements, subject safety, protocol procedures, and for data accuracy. The Case Report Forms and images will be reviewed and retrieved during the monitoring visit. All source documentation will remain in the subject's files at the site.

Review and Analysis of all data collected will be conducted by the Sponsor or designee as described for this protocol with the following data:

Demography and Baseline Measurements

Demographic and baseline/screening measurements (e.g., age, weight, clinical VLS signs and digital images) will be collected and descriptively presented.

Treatment Visits

Clinical VLS signs as assessed by the study investigator, photographs of the treated region, and NSR scores will be collected and compared to baseline to assess efficacy and safety. Any potential adverse events will be documented.

Follow-up Visit Measurements

Follow-up measurements, efficacy and satisfaction assessment scores, and digital images will be used for comparative measurements with their respective data at baseline. Primary endpoints will be evaluated at the 6-week, 3-month, 6-month and 12-month follow-up visit.

Safety

Safety of device procedure will be evaluated throughout the study. Any side effects to the treated area will be reported by the subject, the study investigator and the research staff. The occurrence and severity of all complications from the start of the study will be recorded.

ADVERSE EVENTS (AE)

An adverse event (AE) is any adverse change in health or side effect that occurs in a study participant during their participation in the study.

Anticipated Adverse Effects

An adverse event (AE) is any undesired clinical occurrence in a study subject as indicated by signs, symptoms, illnesses, events that develop or worsen in severity in association with the study when deemed by the Investigator to be related to use of the device or study procedures.

Anticipated post-treatment adverse effects which could result from the CO₂RE treatment include pain, swelling, bruising (ecchymosis), blistering, burn, and infection.

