The Investigator will document all adverse signs and symptoms regardless of severity or frequency that are either volunteered by subjects or observed during the course of the study that are related to the device. The Investigator will also record adverse experiences of subjects resulting from concurrent illnesses, reactions to concurrent medications, or progression of disease states that the Investigator deems related to the device. Included in the description will be the nature of the sign or symptom, the date of onset, whether the event was serious, the severity, the relationship to study procedures or investigational device, the action taken, the date of resolution, and the outcome. The Principal Investigator will determine the relationship of the adverse device effect to the investigational device.

Unanticipated Adverse Device Effects

For device studies, part 21 CRF 812.3(s) uses the term unanticipated adverse device effect which is defined as any serious adverse effect on health or safety or any life-threatening problem or death caused by, or associated with, a device, if that effect, problem, or death was not previously identified in nature, severity, or degree of incidence in the investigational plan or application (including a supplementary plan or application), or any other unanticipated serious problem associated with a device that relates to the rights, safety, or welfare of subjects.

All unanticipated adverse effects will be graded as follows:

Mild: Sign or symptom, usually transient, non-life-threatening requiring no special treatment and generally not interfering with usual activities.

Moderate: Sign or symptom, non-life-threatening which may be ameliorated by simple therapeutic measures and may interfere with usual activity.

Severe: Sign or symptom that is intense or debilitating but non-life-threatening and that interferes with usual activities. Recovery is usually aided by therapeutic measures and the discontinuation of the study device may be required.

Serious: Any untoward medical occurrence that at any time results in death or life-threatening illness, resulting in persistent or significant disability/incapacity.

The relationship of the adverse effect to the study is defined as follows:

Probable: An adverse event has a strong temporal relationship to study device, and another etiology is unlikely or significantly less likely.

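### The protocol defines an adverse event twice, once with and once without a relatedness condition, and no text says which governs, so the scope of the safety endpoint is open

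*Protocol*

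**What the plan says.** The synopsis and the Secondary Safety Endpoints section count adverse events over the course of the study and describe their severity and type. Neither attaches a relatedness condition.

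The term is defined in two places:

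- Directly under Adverse Events (AE): "any adverse change in health or side effect that occurs in a study participant during their participation in the study".
- Under Anticipated Adverse Effects, for the same term: an undesired clinical occurrence "when deemed by the Investigator to be related to use of the device or study procedures".

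The recording instructions follow under Anticipated Adverse Effects:

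- The first sentence has the investigator document adverse signs and symptoms "that are either volunteered by subjects or observed during the course of the study that are related to the device".
- The second adds adverse experiences "resulting from concurrent illnesses, reactions to concurrent medications, or progression of disease states that the Investigator deems related to the device".
- The third lists what each record holds, including "whether the event was serious, the severity, the relationship to study procedures or investigational device".

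Elsewhere the wording is wider. Under Data Analysis, the Treatment Visits section says "Any potential adverse events will be documented" and the Safety section says "The occurrence and severity of all complications from the start of the study will be recorded". Table 2 provides for adverse-event interviews across the whole study. The Follow-up Visits section asks for a review of medication, medical history and adverse events. The relationship scale has four categories, among them Probably not and Not related.

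The anticipated effects "include pain, swelling, bruising (ecchymosis), blistering, burn, and infection". The severity grade definitions, under Unanticipated Adverse Device Effects, are introduced for unanticipated effects only.

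**The concern.** The endpoint is a count, and the count depends on what qualifies for entry. Under one definition every adverse change in health is entered and relatedness is then rated. Under the other, the investigator judges relatedness first and only events that pass become adverse events. Two of up to four sites could follow different sentences, both comply with the protocol, and produce counts that do not mean the same thing.

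This is not a matter that a statistical analysis plan can settle later. An analysis plan can select a subset of recorded events, but it cannot restore events that were never entered. In a single-group study there is no comparator rate, so a relatedness filter at entry also removes the data that would let someone else review the investigator's judgement.

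**Working it through.** The documents give no event rates, so this is a comparison of texts plus two small counts.

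**Step 1. Apply each rule to three kinds of event.**

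| Event | First definition | Second definition | First recording sentence |
|---|---|---|---|
| Judged related to the laser | Adverse event | Adverse event | To be documented |
| Biopsy complication judged related to the biopsy, not to the laser | Adverse event | Adverse event | Not covered |
| Intercurrent event judged unrelated to both | Adverse event | Not an adverse event | Not covered |

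The three texts agree only on the first row. The definitions disagree on the third row. The recording sentence departs from both definitions on the second.

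**Step 2. Does the second recording sentence close the gap?** Its final clause on device-relatedness may attach to disease progression alone. Concurrent illness and drug reactions are then recorded whatever their cause. If the clause attaches to all three items, nothing unrelated to the device is added. Grammar allows both. Neither reading brings in biopsy complications as such.

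**Step 3. Does the wider wording decide the matter?** The Safety sentence on complications has no relatedness condition and avoids the disputed term, so it conflicts with the narrow sentences. The Treatment Visits sentence points the same way. Table 2 and the adverse-event part of the follow-up review use the disputed term and so take whichever meaning it has. No text ranks one rule above another.

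**Step 4. What does the relationship scale show?** Of its four categories, two (Probably not and Not related) describe events with a weak or absent link to the device. They fit the first definition naturally. They are not necessarily empty under the second, because a procedure-related event could be rated Not related to the device. The scale is therefore supporting evidence, not proof. All four categories are worded for the device, although the record is to hold the relationship to study procedures or device.

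**Step 5. Count the exposed procedures.** The Vulvar Biopsy Procedure section schedules biopsies at baseline, 6 weeks and 6 months, in up to 10 subjects:

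- scheduled biopsies: 10 x 3 = 30 at most;
- before any laser exposure: 10 x 1 = 10 at most;
- after the final treatment: 10 x 2 = 20 at most.

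The same section lists pain, bleeding, infection, scarring and anaesthetic allergy among the risks. A complication of a baseline biopsy that arises before the first treatment cannot be device-related, so it falls outside the first recording sentence. Biopsy is optional, so fewer may be done. An inadequate sample may need a repeat, so 30 is the scheduled number and not a ceiling.

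**Step 6. Check severity.** Six anticipated effects are listed, and the mild, moderate and severe definitions are not stated to apply to any of them. Pain does have a 0 to 10 scale (Appendix V) and a 0 to 3 diary discomfort scale (Appendix VI), though neither is labelled an adverse-event grade. That leaves 6 - 1 = 5 effects with no stated severity scale. Serious also appears in the grade list, while the third recording sentence treats seriousness and severity as separate items.

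**The case against.** The strongest reply is that the protocol as a whole already captures widely. The Safety sentence on complications runs from the start of the study and, on its plain words, reaches baseline biopsy complications. The follow-up review of medical history and medication would leave a trace of many intercurrent illnesses. Table 2 also applies whenever a subject raises a safety concern. The first recording sentence does not say *only*, and the second begins by adding to it. The adverse event forms mentioned under Case Report Forms are not shown and may be broad.

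Much of this stands, and it limits the consequence. A reader might infer that the protocol restricts recording to device-related events, or that biopsy complications and unrelated illness would be lost altogether. The documents do not support either inference: they give conflicting rules, and some record may well exist. But a trace in the medical history is not an entry in the adverse-event count, and a wide rule in one section does not cancel a narrow one in another.

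Three further inferences should be resisted:

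- That the principal investigator's duty to judge relationship to the device contradicts the wider record. That sentence concerns an adverse device effect, which is a different term.
- That the Not related category proves the first definition governs. Step 4 shows why it does not.
- That all six anticipated effects lack any severity measure. Pain has its own scales.

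It can also be said that the contradiction calls only for reconciliation, not for full capture. That is fair as logic. The reason to reconcile towards the wider definition is practical: a wide record can be narrowed at analysis, and a narrow one cannot be widened.

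**Conclusion.** The point holds. One term carries two incompatible definitions, the first recording sentence is narrower than both, the second is ambiguous, and the wider statements under Data Analysis conflict with the narrow ones. The safety endpoint therefore depends on which sentence a site follows.

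The exposure can be described but the under-count cannot be sized. Events judged unrelated, and complications of up to 30 scheduled biopsies, could be left out of the count by a site that follows the first recording sentence. The documents do not show that any site would do so.

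The conclusion rests on the protocol text alone and assumes that the unseen adverse event forms do not settle the scope. It should be fixed. The severity-grade wording is a secondary drafting fault and does not itself bear on scope.

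**What to change.** - Keep the definition under Adverse Events (AE) as the only one.
- Delete the relatedness condition from the second definition and from both recording sentences under Anticipated Adverse Effects.
- Record every adverse event, with its relationship to the device and its relationship to study procedures as recorded attributes. Word the categories so that they work for each.
- As a secondary correction, apply the mild, moderate and severe definitions to all adverse events and take Serious out of the grade list, keeping it as a separate field.

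How related events are then tabulated can be left to the analysis plan.

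The cost is protocol and case report form wording, some additional entries at the sites, and higher reported event counts. The last is a presentational cost: the count would include events that the narrow reading would have kept out.
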